#### 8.2.2.1 Lu-edotreotide Whole Body Planar Scintigraphy

Lu-edotreotide whole body 2D planar images will be performed in anterior and posterior projection, in conjunction with transmission/blank scan using Co or 99mTc sheet source or if available at the site whole body low dose CT scan for attenuation correction (pre-dose) and an external calibration source. Serial scans will be obtained at four points of time after first dosing (D1, day 0) of Lu-edotreotide: 0.5 h (prior to voiding), 6 h, 24 h and 72-96 h post-infusion. An additional Lu whole body planar imaging 7 days post infusion may be performed at investigator's discretion.

Scintigraphy results will be used to determine Lu-edotreotide traditional 2D dosimetry (reference method), with emphasis to kidney (safety) and target tumours (efficacy).

In selected patients, the accuracy of AD predictions made based on the first cycle will be verified by repeated dosimetry in cycles D2 – D4 (Sub-study A: verification of the accuracy of AD extrapolation based on AD determined after D1).

#### 8.2.2.2 Lu-edotreotide Abdominal SPECT/CT

Abdominal SPECT/CT scans, covering kidneys and liver will be acquired in a supine position (usually 1 - 2 bed positions), 24 h after each infusion of Lu-edotreotide (D1 - D4). The scan following D1 will be quantitatively reconstructed, to yield absolute activity concentrations (Bq/ml) for 2D/3D hybrid dosimetry. The scans from D2 – D4 will be analysed qualitatively only, to demonstrate tumour targeting of Lu-edotreotide. In subjects participating in Sub-study A, quantitative reconstruction will be made for all cycles (D1 – D4).

After the first dosing (D1) a SPECT/CT scan will be performed. CT-derived information data from this scan will be used for attenuation and scatter correction.

##### a) Tumour targeting

Tumour targeting will be assessed by demonstration of Lu-edotreotide binding inside or in the vicinity of the target lesion, seen on structural imaging using SPECT/CT acquired 24 h post-infusion.

##### b) 2D/3D hybrid dosimetry

To take superimposition and self-absorption of abdominal organs into consideration, quantitatively reconstructed abdominal SPECT images (Bq/mL) from a single time point (24 h p. i.) of the first dose (D1) will be used to correct 2D planar dosimetry results (reference method), with emphasis to kidney and target tumours.

#### 8.2.2.3 Serial Lu-edotreotide SPECT/CT, (Sub-study B, only)

At sites, where 3D dosimetry is performed as routine, or research methodology, serial SPECT/CT imaging covering kidneys and tumour will be acquired in a supine position (usually 2 bed positions), in addition to the mandatory planar acquisitions (see Section 8.2.2.1). SPECT/CT images will be acquired subsequent to planar images and quantitatively reconstructed as described under Section 8.2.2.2.

#### 8.2.2.4 Pharmacokinetic Urine Analysis (Sub-study C, only)

At selected sites, urine will be collected after any one of the 4 administrations of Lu-edotreotide from all voids of patients in the Lu-edotreotide arm, beginning immediately post-dose (0 min) to 1 hour, and in intervals of 1-6, 6-24 and 24-48 hours post-injection in a subgroup of 20 patients, to assess *in-vivo* stability of Lu-edotreotide. Volume and radioactivity content of these voids should be recorded up to 48 hours. Radioactivity concentrations will be measured with a calibrated well-type gamma-counter. Urine will be analysed using radio-HPLC in order to investigate the radiochemical purity of the eliminated compound.

#### 8.2.2.5 Bone Marrow Dosimetry (Sub-study C, only)

As the radioactivity in blood was shown to be similar to that in bone marrow (Forrer et al., 2009), bone marrow dosimetry will be assessed by measuring radioactivity in blood samples at 0 min, 10 min,

30 min, 1 h, 3 h, 6 h, 24 h, 48 h, 3 d, and 7 d post injection during any one of the 4 administrations of  $^{177}\text{Lu}$ -edotreotide in a subgroup of 20 patients in the  $^{177}\text{Lu}$ -edotreotide arm at selected sites only.

### 8.2.3 Health-Related Quality of Life (HRQL) and Symptom Control

To evaluate HRQL, self-rating questionnaires will have to be completed by the patient at baseline, and then monthly until month 12, thereafter in 3-monthly intervals until diagnosis of progression or end of study. Completion will be made prior to the administration of study medication, if applicable for this visit.

#### 8.2.3.1 EORTC QLQ-C30

The QLQ-C30 questionnaire (version 3.0, in local language) will be used for the assessment of the general health state. It will not be considered for the diagnosis of progression or symptomatic tumour response (see Section 9.2.2).

#### 8.2.3.2 EORTC QLQ-GI.NET21

The QLQ-GI.NET21 questionnaire (in local language) will be used for the assessment of symptomatic response to therapy, as well as for the diagnosis of symptomatic progression (see Section 9.2.2). In patients with elevated baseline GI.NET21 score, changes in the score will be classified as follows: Complete symptomatic response (CRs): normalisation of score; partial response (PRs): decrease  $\geq 50\%$  from baseline score; symptomatically stable disease (SDs): An increase by  $< 25\%$  or decrease by  $< 50\%$  from baseline scores. Symptomatic progression (PDs) will be defined as an increase in the GI.NET21 score of  $\geq 25\%$  from baseline, or compared to prior examination, in patients, where an initial improvement following therapy has been observed.

### 8.2.4 Assessment of Progression-free Survival

#### Primary endpoint

The primary endpoint is progression-free survival (PFS), determined as time elapsed between randomisation and the date of first objective report of tumour progression (evaluated by RECIST criteria, 1.1), or death. Diagnosis of progression will be established based on radiological information from morphological imaging (MRI / CT) using RECIST 1.1 (Eisenhauer et al. 2009). Status of disease will be defined as one of the following options: Complete response (CR), partial response (PR), stable disease (SD), or progressive disease (PD).

In addition to the evaluation by local investigators pseudonymised images will be transferred to the ICL (see Section 8.7), and analysed by independent radiologists not involved in the study in a blinded fashion in duplicate, with adjudication in case of discordance. In case of discordance reads, a third independent radiologist will act as an adjudicator.

A detailed description of the process of image handling, analysis and documentation will be outlined in a separate document, the image review charter (IRC).

## **8.3 Safety**

### **8.3.1 Baseline Findings**

#### **8.3.1.1 Definition of Baseline Finding**

##### Definition of a baseline finding

A baseline finding is defined as any untoward medical condition in a study patient who has signed the informed consent form but not yet received the first dose of the study drug. This includes conditions stabilised by treatment. By definition, a baseline finding cannot be causally related to study drug; however, it may be causally related to the study (e.g., caused by study-conduct-related investigations).

##### Differentiation between medical / surgical history and baseline findings

Conditions which started before signature of informed consent and for which no symptoms or treatment are present until the first administration of study drug (e.g., seasonal allergy without acute complaints) are recorded as medical / surgical history.

Conditions which started before signature of informed consent and for which new or worsening symptoms or further treatment are present between signature of informed consent and first administration of study drug (e.g., allergic pollinosis) are recorded as baseline findings.

##### Differentiation between baseline findings and adverse events

Conditions (e.g., abnormal physical examination findings, symptoms, diseases, laboratory, ECG) present before the first administration of study drug will be documented as baseline findings.

Conditions which started or deteriorated after the first administration of study drug will be documented as adverse events.

##### Pregnancy

Following the existing international guidelines on embryo-foetal Risk Mitigation and Risk Assessment of Medicinal and Investigational Medicinal Products on Human Reproduction and Lactation and in consideration with the absence of adequate data from the use of the reference study drug in pregnant women and its effects including known embryotoxicity and fetal toxicity as well as considering the known risks of radiation exposure to the embryo or foetus from therapeutic procedures with the administration of radioactive pharmaceuticals, highly effective contraceptive methods that can achieve a failure of less than 1% per year when used consistently and correctly are considered to be used in this study. Female patients of childbearing potential as well as male patients having female partners of childbearing potential, unless surgically/permanently sterile (bilateral tubal occlusion, hysterectomy, or vasectomy), will be excluded from participation in the study unless they are willing to: practice full and true sexual abstinence, or use highly effective contraception in combination with a barrier method of contraception (e.g. condom). Contraception methods that are considered highly effective are: oral or non-oral (injected or implanted) non-oestrogen progesterone-based hormonal

method; oral, intravaginal, or transdermal combined oestrogen and progesterone-based hormonal method; and/or IUD, and/or IUS. Sexual abstinence or the contraception methods described above must be followed throughout the entire study period and for 56 days after treatment in the everolimus group and 66 days in the PRRT group (10 half-lives of  $^{177}\text{Lu}$ ) after the last treatment cycle. True abstinence may be practised if this is in line with the preferred and usual lifestyle of the subject. Periodic abstinence (e.g. calendar, ovulation, symptothermal, post-ovulation methods), declaration of abstinence for the duration of exposure to IMP, and withdrawal are *not* acceptable methods of contraception. A partner who has a medically successful vasectomy is a highly effective birth control method provided the partner is the sole sexual partner of the female patient of childbearing potential.

Pregnancy is rather unlikely due to study design and presents an exclusion criterion for this study. Adequate pregnancy testing will be performed at regular intervals throughout the study (see Section 8.3.6). Should it nevertheless emerge, it will not be classified as an SAE except in cases where it can be shown that the effectiveness of the contraception was affected by the IMP/RP. A female patient who becomes pregnant during the treatment phase of the study must be discontinued from study treatment. All pregnancy cases (pregnant patient or a male patient who has impregnated a partner) except those emerging after 80 days (66 days per exclusion criteria and 14 days additional waiting period) after the last treatment cycle in the PRRT group and 70 days (56 days per exclusion criteria and 14 days additional waiting period) after treatment in the everolimus group, will be monitored and followed up in regular intervals in order to identify adverse events especially fulfilling the criteria for an SAE. If a pregnant patient or a male patient who has impregnated a partner withdraws from the study during the pregnancy, the pregnant patient/partner will be monitored and followed up on at regular intervals in order to identify adverse events especially fulfilling the criteria for an SAE until the end of the pregnancy. A pregnant patient will not have any further radiation-related follow-up assessments or other follow-up assessments that may interfere with the pregnancy, determined by investigator discretion.

### 8.3.1.2 Categories, Assessments and Documentation of Baseline Findings

The date and time of the first acute occurrence of the event is documented as the onset.

If the baseline finding is "continuing" into the treatment phase, no AE is to be recorded if, after start of study treatment, the event has the same or milder pattern and intensity/severity. If the finding worsens in terms of either the pattern or intensity/severity after study drug administration, the event must be documented as an AE.

If the event is concluded, this should be recorded in the CRF ("resolved"). If the event vanishes but re-occurs during treatment, an AE with a start date of its re-occurrence should be entered.

All baseline findings will be assessed and documented by the investigator according to the following categories:

- Seriousness: for each baseline finding, the seriousness must be determined according to the criteria given in Section 8.3.2.5. If serious, the baseline finding has to be handled in the same way as an SAE.
- Intensity/Severity

- Specific drug treatment
- Specific non-drug treatment
- Causal relationship to study conduct
- Outcome

The intensity/severity of an event, the causal relationship to study conduct, and the outcome of the baseline finding should be classified according to the same categories used for AEs, as specified in Section [8.3.2](#).

### **8.3.1.3 Serious Baseline Findings**

Baseline findings will be regarded as serious if they meet the criteria used for defining serious adverse events (SAEs) (see Section [8.3.2.5](#)).

Serious baseline findings will be reported on the SAE form described in Section [8.3.2.5](#).

## **8.3.2 Adverse Events**

### **8.3.2.1 Definition of Adverse Event**

The definition below follow International Conference on Harmonisation (ICH) – Good Clinical Practice (GCP) (see also ICH Guideline for Clinical Safety Data Management: Definitions and Standards for Expedited Reporting):

#### Adverse event (AE)

Any untoward medical occurrence in a patient or clinical investigation subject administered a pharmaceutical product and which does not necessarily have a causal relationship with this treatment. An AE can therefore be any unfavourable and unintended sign (including an abnormal laboratory finding), symptom, or disease temporally associated with the use of a medicinal (investigational) product, whether or not considered related to the medicinal (investigational) product.

By definition, for this study, all AEs are regarded as 'treatment emergent', i.e., not seen before treatment or, if already present before treatment, worsened after start of treatment. See Section [8.3.2.6](#) for exemptions.

### **8.3.2.2 Categories for Adverse Event Assessment**

All AEs will be assessed and documented by the investigator according to the categories detailed below. NCI-CTCAE version 4.03 will be used for this purpose.

#### **Seriousness**

For each AE, the seriousness must be determined according to the criteria given in Section [8.3.2.5](#).

### ***Intensity/severity***

The intensity of an AE is classified according to NCI-CTCAE version 4.03, taking into account the possible range of the intensity of the event (see Section [8.3.2.3](#)).

- NCI-CTCAE Grade 1 (mild)
- NCI-CTCAE Grade 2 (moderate)
- NCI-CTCAE Grade 3 (severe)
- NCI-CTCAE Grade 4 (life-threatening)
- NCI-CTCAE Grade 5 (fatal)

An AE should be documented with the applicable diagnosis, if possible (rather than as a symptom, sign, or laboratory finding).

### ***Main pattern***

The main pattern of the AE is to be documented as follows:

Every drug administration:	Events that occur in a clear time relationship to every study drug administration
Intermittent:	Regular or irregular repeating events that are clearly of the same kind and same cause, but not clearly time related to study drug administration
Continuous:	Events that are continuously present within the whole time period which is covered by the form, but not clearly time related to study drug administration
Other:	All other patterns, need to be specified in the following text field

### **Study drug action**

Any potential study drug action to resolve the AEs is to be documented as follows

- Drug withdrawn
- Dose reduced
- Dose not changed
- Other action (stopped: definitely, temporarily with exact dates )

### ***Drug treatment***

### ***Non-drug treatment***

### ***Causal relationship to study drug***

The assessment of a possible causal relationship between the AE and the administration of the study drug is based on the following question:

“Is there a reasonable likelihood that the event was caused by the study drug?”

Possible answers are:

- Related (plausible time relationship to the administration of IMP/RP. No plausible explanation by underlying/concurrent disease or other drugs/events),
- Possible (plausible time relationship to the administration of IMP/RP, but the AE can be also plausibly explained by the underlying/concurrent disease or other medicinal products/events),
- Unlikely (unlikely temporal relationship to the administration of IMP/RP. Other medicinal products, events, and the underlying/concurrent disease provide a plausible explanation)
- Not related (clear evidence that the AE is not connected to the IMP/RP administration)
- Not assessable (no evaluation possible based on present data, additional clarification and follow-up necessary)

### ***Causal relationship to study conduct***

The assessment of a possible causal relationship between the AE and the study conduct other than the relationship to study drug is based on the following question:

“Is there a reasonable likelihood that the event was caused by the study conduct?”

- Possible answers are “related”, “not related”, “not assessable.”

### ***Outcome***

The outcome of the AE is to be documented as follows:

- recovered
- recovered with sequelae, with additional details
- ongoing
- fatal
- unknown

### **8.3.2.3 Assessments and Documentation of Adverse Events**

All adverse events which occur up to EOS, both those observed by study site personnel and those spontaneously reported by study patients, must be recorded on the ‘adverse event’ page(s) in the

CRF regardless of causality. AEs ongoing at EOS have to be followed up until resolved or for a period up to a maximum of 30 days by the investigator.

If an adverse event fulfils any of the criteria for a SAE, both the adverse event pages of the CRF and the Serious Adverse Event Form must be completed. SAEs are recorded for the entire duration of the study. For details of how to report SAEs see Section [8.3.2.5](#).

For both Serious and Non-serious AEs, documentation must be supported by an entry in the patient's hospital notes. Required information includes: the type of adverse event, seriousness of the event, start date, date of resolution, actions required, outcome, and an assessment of its relationship to study drug and an estimate of its severity (using NCI-CTCAE, version 4.03). NCI-CTCAE severity will be marked in the SAE Report Form using the numeric grades: grade 1 (mild), grade 2 (moderate), grade 3 (severe), grade 4 (life-threatening) and grade 5 (fatal).

All abnormal laboratory results, which are considered to be clinically relevant by the investigator, should also be recorded as adverse events. If an abnormal laboratory result meets any of the criteria for a SAE, this must also be reported on a Serious Adverse Event Form.

An AE should be documented with the applicable diagnosis, if possible (rather than as a symptom, sign, or laboratory finding).

All adverse events that meet the criteria for serious require the completion of a SAE Report Form, in addition to being recorded on the AE pages of the patients' CRF. This applies to all SAEs, whether or not they were considered to be related to study treatment.

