## **4.6 End of the Study**

For regulatory purposes, the end of the study is defined as the last visit of the last patient or the last date of follow-up of toxicities, if required (whichever is later).

The end of study for each individual patient is the visit at month 30, unless disease progression, withdrawal from the study, or death occurs earlier.

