#### 6.1.1 Prohibited Medications

Patients will not be permitted to enter the study if they have received any of the following therapies:

- Prior exposure to any PRRT, including Lu-edotreotide, Y-edotreotide or other SSTR-targeting agents (e.g. Lu-octreotate or high-dose In-pentetreotide)
- Prior mTOR inhibitor therapy

- Prior EFR (external field radiation) to GEP-NET lesions or radioembolisation therapy (e.g.  $^{90}\text{Y}$  microsphere,  $^{131}\text{I}$ -lipiodol) administration to the liver
- Prior therapy with an investigational compound and/or medical device within 30 days or 5 half-life periods (whichever is longer) prior to randomisation.
- Any new cancer treatment between screening and randomisation

The following therapies are prohibited from 4 weeks before randomisation until the end of the study: chemotherapy, immunotherapy, interferon, radiation therapy, chemo-embolisation, bland embolisation, radioembolisation, cyclosporine-A, or any other cancer therapy. In the event that any prohibited medication is given to a patient during the study, any such medication needs to be recorded in the CRF. The patient will then be excluded from further participation.

Subjects in the everolimus group must not receive live vaccines during the study and for eight weeks after final dose. Potent inhibitors of CYP3A4 and PgP, and potent inducers of CYP3A4 are also prohibited for everolimus patients (see Section 6.1.5.2).

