### 8.3.6 Pregnancy Tests

A serum or urine  $\beta$ -HCG pregnancy test will be performed for all female patients of childbearing potential at baseline, within 28 days prior to first study treatment.

Post-menopausal status (for female patients <60 years of age) must be proven by one of the following:

- History of hysterectomy
- Last spontaneous bleeding at least 1 year prior to informed consent and negative  $\beta$ -HCG
- Serum estradiol <20 pg/mL and FSH >40 IU/L

During the course of the study, pregnancy tests will be repeated monthly until end of study in female patients of childbearing potential. At the first dosing visit (D0), a pregnancy test does not need to be

performed if the baseline pregnancy test result is not older than 14 days. Since after month 12 and during the 2nd year (months 12-27), visits are performed in three monthly intervals, female patients of childbearing potential will be provided with pregnancy test strips for the performance of pregnancy tests at home during months: 13, 14, 16, 17, 19, 20, 22, 23, 25, and 26. The study sites/Investigators will collect and register information on the outcome of the tests via telephone contacts.

A female patient who becomes pregnant during the treatment phase of the study must be discontinued from study treatment. SAE reporting/pregnancy reporting and pregnancy monitoring and follow-up will be performed as described in Sections 8.3.1.1 – pregnancy – and 8.3.2.5.

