8.1 Adverse Events

Adverse events prior to the first treatment will be captured for all enrolled patients and reported separately from treatment emergent AEs (TEAEs), as baseline findings.

The number of event episode as well as the count and percentage of patients with at least one event will be determined by treatment arm. The analysis will be presented overall and by maximal severity grades.

This analysis will be tabulated for treatment emergent AEs (TEAEs), Adverse reactions (ARs = AEs at least possibly related to the study drug), Serious TEAEs (TESAEs), Serious ARs (SARs), SARs by possible cause of event, TEAEs by action taken on the study drug (change or discontinuation), TEAEs that led to premature study termination, and Fatal TEAEs.

AEs will also be tabulated according to the primary system organ class (SOC), preferred term (PT) and maximal severity. Patient-based count and percentages will be given by treatment arm for SOC followed by those for PT in descending order of the IMP arm.

In this analysis a patient with several events with identical SOC and PT will be counted only once at the maximal severity.

This analysis will be tabulated for TEAEs, ARs, SAEs, SARs, TEAEs by action taken on the study drug (change or discontinuation), TEAEs that led to premature study termination, and fatal TEAEs.

A summary will also be presented by SOC and PT such as mentioned above by treatment arm for all pooled severity grades and pooled grades 3 or 4 TEAEs and ARs.

If deemed appropriate other analysis, table and summaries can be presented to further explore the pattern of adverse events.

All AEs will be listed.

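### New adverse events are recorded only up to EOS, leaving little or no post-dose window for everolimus, and the SAP tabulates crude percentages over observation times of unequal length

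*Protocol*

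**What the plan says.** **End of collection.** Protocol 8.3.2.3 covers "All adverse events which occur up to EOS". Events already ongoing at that point are followed until resolved or "for a period up to a maximum of 30 days by the investigator". The same section adds that "SAEs are recorded for the entire duration of the study". Section 4.6 states: "The end of study for each individual patient is the visit at month 30, unless disease progression, withdrawal from the study, or death occurs earlier". It also defines a separate, later end of study for regulatory purposes. After early withdrawal, section 7.3.11 places the EOS visit within 28 days of discontinuation.

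**Dosing.** The synopsis has everolimus taken daily until progression or EOS, and PRRT given on days 0, 90, 180 and 270. Haematology is checked every two weeks for 8 weeks after each PRRT dose.

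**After EOS.** Section 7.4.1 collects survival, progression, further cancer treatment, late toxicities and secondary malignancies for five years, at 6-monthly contacts.

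**Other post-dose periods.** Contraception is required for 56 days after everolimus and 66 days after PRRT. Everolimus patients "must not receive live vaccines during the study and for eight weeks after final dose". Pregnancies are followed up unless they emerge more than 80 days after the last PRRT cycle or "70 days (56 days per exclusion criteria and 14 days additional waiting period) after treatment in the everolimus group".

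**Pregnancy testing.** Sections 7.3, 7.3.9 and 8.3.6 require monthly tests until EOS. Section 8.3.6 lists the home tests "during months: 13, 14, 16, 17, 19, 20, 22, 23, 25, and 26".

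**Analysis.** In SAP 8.1, besides the number of episodes, "the count and percentage of patients with at least one event will be determined by treatment arm", overall and by maximal severity. Further AE analyses are optional and unspecified.

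**The concern.** AE capture is tied to EOS and not to the last dose. For everolimus the two nearly coincide, so an event starting in the weeks after the last tablet has no defined route into the AE tables. This would tend to understate everolimus toxicity.

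An AE percentage also depends on how long patients are watched. Observation ends at progression, so the arm with longer PFS is watched longer, and the prespecified tables contain nothing that accounts for this. The two problems need not act in the same direction, so a reader of the tables could not work out the net bias. At stake is the safety comparison that accompanies a positive or negative PFS result.

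**Working it through.** **1. The plan's own figures.** 10 × 6.647 d = 66.5 d (stated 66); 66 + 14 = 80; 56 + 14 = 70; 8 weeks = 56 d; HR = 11/17 = 0.6471. All reproduce.

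**2. Everolimus: days after the last tablet with no collection of new AEs**

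| EOS relative to last tablet | of the 56 days | of the 70 days |
|---|---|---|
| same day (dosed to progression or month 30) | 56 | 70 |
| 28 days later (latest early-withdrawal visit) | 28 | 42 |

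This takes the last tablet as the date of discontinuation. With exponential PFS at median 11 months, the share progressing by month 30 is 1 − exp(−30 ln 2/11) = 0.849.

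**3. PRRT: last dose to EOS.** For a 30-month completer this is 30 × 30.4375 − 270 = 643 days. If progression is found at the next scheduled scan it is about 90 days, or 90 − 14 − 7 = 69 with an early visit and early imaging. Both exceed the 56 days of haematology and the 66-day period. A late or delayed dose can shorten the interval further. The gap therefore concerns patients who leave soon after a dose.

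**4. Observation time.** Inputs are the medians in SAP section 4, Table 2. With λ = ln 2/median, mean time to progression or month 30 is (1 − exp(−30λ))/λ.

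| Arm, median | Mean (months) | Ratio |
|---|---|---|
| Everolimus, 11 | 13.5 | 1 |
| PRRT, 17 | 17.3 | 1.28 |
| PRRT, 22 | 19.4 | 1.44 |
| PRRT, 30 | 21.6 | 1.61 |

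**5. Effect on crude percentages if the AE hazard is equal and constant.** The hazard h is an assumption; the documents give none. P(event seen) = h/(h+λ) × (1 − exp(−30(h+λ))).

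| h per month | Everolimus | PRRT, medians 17 to 30 |
|---|---|---|
| 0.01 | 12.2% | 15.4–19.0% |
| 0.02 | 22.1% | 27.6–33.7% |
| 0.03 | 30.3% | 37.3–45.0% |
| 0.05 | 42.8% | 51.5–60.8% |
| 0.10 | 60.9% | 70.0–79.2% |

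Unequal windows alone give about 3 to 18 points, against PRRT.

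**6. Effect if PRRT events begin only in months 0 to 11** (also an assumption; dosing ends on day 270). With h = 0.02 and 11 in place of 30 in the exponent, PRRT shows 16.0%, 16.8% and 17.5% at medians 17, 22 and 30, against 22.1% for everolimus. The direction reverses.

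**7. A single person-time rate does not solve this.** In scenario 6, mean time at risk for PRRT is (1 − exp(−11(h+λ)))/(h+λ) + exp(−11(h+λ)) × (1 − exp(−19λ))/λ = 14.8, 16.5 and 18.3 months. The rates are 16.0/14.8 = 1.08, 16.8/16.5 = 1.02 and 17.5/18.3 = 0.96 per 100 patient-months, against 2.0 for everolimus. The hazard during the at-risk period is identical, and off-drug months dilute the PRRT rate.

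**8. A common time point does.** With end of collection treated as censoring and h = 0.02, 1 − exp(−0.02t) gives 11.3% at 6 months in both arms, under scenario 5 or 6 and at any PFS median.

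**The case against.** The best case for the plan is that safety capture does not simply stop at EOS. Ongoing events are followed for up to 30 days, SAEs are recorded throughout the study, and late toxicities are collected for five years, including from drop-outs. A reader might infer that late everolimus events and SAEs go uncaptured altogether. The documents do not support that. SAE recording after a patient's own EOS is ambiguous, because 8.3.2.3 does not say which of the two ends of study in 4.6 it means. What stands is that a first contact at 6 months is a poor way to date and attribute an event that began weeks after the last tablet, possibly after another therapy had started.

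A reader might also set the 56-, 66-, 70- and 80-day periods against the AE rule as a contradiction. They serve contraception, vaccination and pregnancy follow-up, differ by arm, and are not AE-reporting windows. They show only that the protocol already works with post-dose periods of that length.

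Nor does the home-test list show that pregnancy goes untested in months 28 to 30. Section 7.3.9 hands out tests at every visit for the following months without visits, and month 30 is tested at EOS. The list is inconsistent with that rule. Pregnancy reporting continues after EOS; only scheduled testing stops.

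Finally, the SAP states no formal between-arm AE test, reports treatment duration in section 6.6 and allows further AE analyses. That limits the consequence, but an optional clause prespecifies nothing.

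**Conclusion.** The point holds in two parts.

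First, there is no fixed collection period for new AEs after the last everolimus tablet. The window is near zero for patients dosed to progression or month 30 and at most 28 days after early withdrawal. The 85% figure assumes exponential PFS at the 11-month median and no drop-out. For PRRT the gap is confined to those who leave soon after a dose, before the week-8 haematology.

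Second, SAP 8.1 prespecifies only crude counts and percentages, although mean observation differs 1.3- to 1.6-fold at the planning medians. It is tempting to conclude that equal toxicity must look worse for the arm with longer PFS. That follows only for equal, constant hazards. With PRRT events confined to the first 11 months, the sign reverses. What can be said is that the crude percentages are not comparable as they stand, and that the artefact could be several points in either direction.

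The pregnancy-testing passages need reconciling; they do not by themselves show a missed test.

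**What to change.** **(a) Protocol 7.3 and 8.3.2.3.** Record new-onset AEs and SAEs until the later of EOS and a stated fixed period after the last dose, for example the 56 and 66 days already in the protocol, by one telephone contact after EOS. State that SAE recording covers this period. Flag events that start after the next anticancer therapy. Enter the already required week 2 to 8 haematology for patients who have left the study.

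**(b) SAP 8.1.** For TEAEs, SAEs and Grade 3/4 events, add time-to-first-event (cumulative incidence) summaries at common time points such as 6 and 12 months, beside the crude percentages. State how end of collection and death are handled. Split any exposure-adjusted rate into on-treatment and off-treatment time.

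**(c) Pregnancy passages.** Reconcile the home-test month list in 8.3.6 with the monthly-until-EOS rule in 7.3, 7.3.9 and 8.3.6. Reconcile the end of testing at EOS with the 70- and 80-day pregnancy follow-up, leaving that follow-up period unchanged.

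**Cost.** One call per patient, a next-therapy flag in the database and extra table columns. Events after EOS may overlap with subsequent treatment, which is the reason for the flag.
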